5.2.3 Safety laboratory parameters

Safety laboratory parameters that will be assessed are listed in Table [5.2.3: 1](#). Sampling time points will be as indicated in the [Flow Chart](#). All analyses will be performed by a central laboratory; the respective reference ranges will be provided in the ISF.

Refer to Table [5.2.3: 2](#) for a list of “minimum required safety laboratory parameters” in the event of force majeure or other disruptive circumstances.

Patients should be fasted for blood sampling for the safety laboratory where that visit is defined as a fasting visit in the [Flow Chart](#); where a non-fasting status is defined, the safety laboratory sample can be collected in a non-fasting status. The fasting status will be recorded for [REDACTED]. Blood samples for safety laboratory parameters should be drawn prior to administration of trial medication.

Instructions regarding sample collection, sample handling / processing and sample shipping will be provided in the central laboratory manual in the ISF.

The central laboratory will provide laboratory reports to the Investigator. It is the responsibility of the Investigator to evaluate these reports. Clinically relevant abnormal findings, as judged by the Investigator, must be reported as AEs (refer to Section [5.2.6](#)).

Laboratory tests may need to be repeated in case of required medical follow-up due to an AE or if a test was not successful due to incorrect specimen handling or storage. Should a patient not fulfil all laboratory requirements to take part in the trial due to a transitional medical condition, the patient may continue in the screening period but cannot be randomised until the re-test of the laboratory result is available to determine the eligibility of the patient (refer to Section [3.3](#)).

In case the criteria for hepatic injury are fulfilled, a number of additional measures will be performed (refer to Section [5.2.6.1.4](#) the DILI checklist which can be downloaded from the electronic data capture [eDC] system, and Appendix [10.2](#)). The amount of blood taken from the patient concerned will be increased due to this additional sampling.

The CKD-EPI formula (isotope dilution mass spectrometry standardised) will be used for reporting eGFR based on serum creatinine.

The central laboratory will transfer the results of the analysis to the Sponsor or delegate. In case qualitative parameters are abnormal, a quantitative analysis will be performed by the central laboratory.

Table 5.2.3: 1 Safety laboratory tests

Category	Test name	Short Name (BI Laboratory Test Code, LBSPID)
Haematology	Haematocrit	HCT
	Haemoglobin	HGB

Category	Test name	Short Name (BI Laboratory Test Code, LBSPID)
	MCV	MCV
	MCH	MCH
	MCHC	MCHC
	RBC count / erythrocytes	RBC
	RBC distribution width (RDW)	RDW
	WBC count / leukocytes	WBC
	Platelet count / thrombocytes	PLTCT
	Reticulocytes	RETABS
Automatic WBC differential (absolute)	Neutrophils	SEGABS
	Eosinophils	EOSABS
	Basophils	BASABS
	Monocytes	MONABS
	Lymphocytes	LYMABS
Coagulation	aPTT	APTTS
	PT	PRTSEC
	INR	INR
	Fibrinogen	FIBR
Clinical chemistry	ALT	SGPT
	Alpha fetoprotein ¹	AFP
	Albumin	ALB
	Alkaline phosphatase	ALKP
	AST	SGOT
	Bilirubin (total)	TBILI
	Bilirubin (direct)	BILID
	Bilirubin (indirect)	BILII
	hs-CRP	CRPHS
	Creatinine, serum	CRE
	CK	CK
	CK-MB ²	CKMBABS
	eGFR	GFRE
	γ-GT	GGT
	Glucose	GLUB
	LDH	LDH
	Lipase	LIPASE
	Phosphatidylethanol (PEth) ³	PETH
	Protein (total)	TPRO
	Troponin I ²	TPONI
Urea (BUN)	UREA	
Uric acid	URIC	
Electrolytes	Bicarbonate	BICARB
	Calcium	CA
	Chloride	CL
	Magnesium	MG
	Phosphate	P
	Potassium	K
	Sodium	NA

Table 5.2.3: 1 contd. Safety laboratory tests

Category	Test name	Short Name (BI Laboratory Test Code, LBSPID)
Lipids ⁴	HDL	HDL
	LDL	LDL
	Cholesterol (total)	CHOL
	Triglycerides	TRIGL
Hormones	Aldosterone ⁵	ALDOSI
	Renin, plasma ⁵	PRCSP
	TSH ⁶	TSH
	Free T3 ⁷	FT3
	Free T4 ⁷	FT4V
Pregnancy test (serum)	Human Chorionic Gonadotropin ⁸	HCG
Pregnancy test (urine)	Human Chorionic Gonadotropin ⁹	Not Applicable
Infections screening ⁶	HCV antibody (qualitative)	HCAB
	HCV RNA PCR ¹⁰	HCVRNA
	HBV surface antigen (qualitative)	HBSAG
	HBV core antibody (qualitative)	HBCAB
	HBV – DNA ¹¹	HBVDNAV
Urine chemistry	Urine albumin	UALBUM
Urinalysis (semi-quantitative)	Urine nitrite	UNIT
	Urine protein	UPROZ
	Urine glucose	UGLU
	Urine ketone	UKET
	Urobilinogen	UROBZ
	Urine bilirubin	UBILI
	Urine blood	UHGB
	Urine leukocyte esterase	ULEUKES
	Urine pH	UPH

- 1 Only performed at screening (Visit 1a) and EoT / ED
- 2 If initial CK is elevated, re-test CK with CK-MB and troponin I
- 3 Not performed at screening (Visit 1a). PEth, an alcohol-specific biomarker, will be measured during the treatment period for data analysis purposes
- 4 Not performed at screening (Visit 1a)
- 5 Not performed at screening (Visit 1a) or Visits 9, 10 or EoS; collect seated after patient seated for at least 5 to 15 minutes, and once patient has been out of bed for at least 2 hours
- 6 Only performed at screening (Visit 1a)
- 7 Reflex in case of abnormal TSH
- 8 WOCBP only; only at Visit 1a, and as a reflex if urine testing is positive
- 9 WOCBP only, Visit 2 onwards. Measured locally at the site every 4 weeks using a pregnancy test kit provided by the central laboratory. Serum pregnancy testing will be done as a reflex if urine testing is positive (see above). Pregnancy testing at dosing visits should be completed prior to administration of the trial medication
- 10 Reflex in case of positive HCV antibody and / or HCV infection that has been treated in the past. Per central laboratory assay, if HCV RNA is < 15 IU / ml at screening (Visit 1a), eligibility criteria are met
- 11 Reflex in case of positive HBV core antibody and negative HBV surface antigen. Per central laboratory assay, if HBV DNA is < 20 IU / ml at screening (Visit 1a), eligibility criteria are met

Table 5.2.3: 2 Minimum required safety laboratory tests (force majeure / other disruptive circumstances)

Category	Test name	Short Name (BI Laboratory Test Code, LBSPID)
Haematology	Haemoglobin	HGB
	RBC count / erythrocytes	RBC
	WBC count / leukocytes	WBC
	Platelet count / thrombocytes	PLTCT
Clinical chemistry	ALT	SGPT
	Albumin	ALB
	Alkaline phosphatase	ALKP
	AST	SGOT
	Bilirubin (total)	TBILI
	Creatinine	CRE
	Potassium	K
Sodium	NA	

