Trial Periods	Screening ¹			Randomised Treatment									Follow-Up	
	1a ¹	1b ¹	1c ¹	2 ²	3	4	5	6	7	8	9	10	EoT / ED ³	EoS ³
Week	-6			R	1	2	4	6	8	12	16	20	24	28
Day	-42			1	8	15	29	43	57	85	113	141	169	197
Time window for visits (days)	See footnote 1			N/A	+ 2	+ 2	+ 2	± 3	± 3	± 5	± 5	± 5	± 5	± 5
Fasting status ⁴	NF	F	F	F	NF	NF	F	NF	F	NF	NF	NF	F	F
Informed consent	x													
Register patient in IRT system via IRT call	x													
Demographics ⁵	x													
Medical history / baseline conditions ⁵	x													
Concomitant therapy	x	x	x	x	x	x	x	x	x	x	x	x	x	x
Anthropometric measures ⁶	x			x	x	x	x	x	x	x	x	x	x	x
Vital signs ⁷	x			x ²³	x ²³	x ²³	x ²³	x	x	x	x	x	x	x
Physical examination ⁸	x ²²			(x)	(x)	(x)	(x)	(x)	x	(x)	(x)	(x)	x	(x)
Resting 12-lead ECG ⁷	x			x ²³	x ²³	x ²³	x ²³	x	x	x	x	x	x	x
Safety laboratory sampling	x			x	x	x	x		x	x	x	x	x	x
Pregnancy testing ⁹	x _s			x _u			x _u		x _u	x _u				
Gastroscopy ^{1, 10}		x												
Hepatic venous pressure gradient (HVPG) ^{1, 11}			x						x				x	
Ultrasound (liver and spleen) ^{1, 12}			x				x		x				x	x
Review of in-/exclusion criteria	x	x	x	x										

FLOW CHART contd.

Trial Periods	Screening ¹			Randomised Treatment									Follow-Up	
	1a ¹	1b ¹	1c ¹	2 ²	3	4	5	6	7	8	9	10	EoT / ED ³	EoS ³
Week	-6			R	1	2	4	6	8	12	16	20	24	28
Day	-42			1	8	15	29	43	57	85	113	141	169	197
Time window for visits (days)	See footnote 1			N/A	+ 2	+ 2	+ 2	± 3	± 3	± 5	± 5	± 5	± 5	± 5
Fasting status ⁴	NF	F	F	F	NF	NF	F	NF	F	NF	NF	NF	F	F
Randomisation				x										
IRT call				x	x	x	x	x	x	x	x	x	x	
Dispense trial medication				x	x	x	x	x	x	x	x	x		
Dose-titration ¹⁴				x	x	x								
Train patient (home BP and HR monitoring) ¹⁵				x	(x)									
Home BP and HR monitoring (by patient) ¹⁵				x	→	→	→	→	→	→	→	→	→	→
Biobanking sampling ¹⁹				x					x				x	
PRO completion (EQ-5D-5L, SF-36v2, CLDQ) ²⁰				x									x	
All AEs / SAEs / AESIs ²¹	x	x	x	x	x	x	x	x	x	x	x	x	x	x
Collect trial medication					x	x	x	x	x	x	x	x	x	
Compliance check					x	x	x	x	x	x	x	x	x	
End of trial medication													x	
Completion of patient participation														x

Footnotes:

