1. The screening period consists of 3 visits (Visits 1a/b/c). These visits should ideally be completed within a period of 4 weeks, but a maximum of 6 weeks (-42 days) will be permitted. There is no minimum duration. A patient can proceed from one visit to the next as soon as all results from the previous visit are available and if he / she remains eligible for the trial. Visit 1b and 1c can be performed on the same day; in that case, the gastroscopy must be performed prior to the HVPG measurement. The ultrasound and [REDACTED] can be performed at either Visit 1b or 1c. Refer to Sections [5.1.1](#), [5.1.2](#), [5.2.5.1](#), [5.2.5.2](#) and [6.2.1](#)
2. Visit 2 = randomisation / Day 1 of trial medication. All assessments at this visit (excluding post-dose vital signs and ECGs, [REDACTED] refer to Sections [5.2.4](#), [5.6.1](#), [6.2](#) and Appendix [10.1](#)) should be completed before the first dose of trial medication is administered
3. Patients who complete 24 weeks of treatment will have an End of Treatment (EoT) visit, followed 4 weeks later by an End of Study (EoS) visit. The last dose of trial medication will be administered in the evening of the day before the EoT visit. Patients who discontinue trial medication prematurely will have an Early Discontinuation (ED) visit completed instead of the planned treatment period visit. The ED visit should be performed within 7 days of discontinuing the trial medication, followed 4 weeks later by an EoS visit. Refer to Section [6.2.2.1](#) for details of assessments that should be performed during an ED visit and the EoS visit that follows it
4. Fasting status: F = fasting (i.e. overnight fast, no food or drink, except water), NF = non-fasting
5. For further details refer to Section [6.2.1](#)
6. Anthropometric measures = height (measured at Visit 1a only), weight, and waist and hip circumference. Refer to Section [5.2.1.1](#)
7. Measurement of vital signs should precede the 12-lead ECG, and measurement of the 12-lead ECG should precede blood sampling and intake of trial medication at visits where a single ECG is required. The 12-lead ECG should be performed after the patient has rested for at least 5 minutes in a supine position. From Visit 2 onwards, the patients home BP monitoring equipment should be used in the clinic to measure vital signs (refer to Sections [5.2.2](#), [5.2.2.1](#) and [5.2.4](#))

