8. At Visits 1a, 7 and at the EoT / ED visit, a complete physical examination is required. At all other marked visits, a physical examination is only required if the patient reports symptoms. Refer to Section [5.2.1](#)
9. Pregnancy testing required in women of child-bearing potential (WOCBP) only. x_s = serum testing; x_u = urine testing. Serum pregnancy will be done at screening (Visit 1a) and as a reflex when urine testing is positive. Pregnancy testing at dosing visits should be completed prior to administration of trial medication. Refer to Section [5.2.3](#)
10. Refer to Section [5.2.5.2](#) for details regarding the necessity for a gastroscopy at Visit 1b
11. For further details regarding the HVPG measurement, refer to Section [5.1.1](#)
12. For further details regarding ultrasound of the liver and spleen, refer to Section [5.2.5.1](#)
13. [REDACTED]
14. For further details regarding dose-titration, refer to Section [4.1.4](#)
15. Electronic home BP monitoring equipment will be provided for a patient to measure BP and HR on a daily basis from Visit 2 (refer to Section [5.2.2.1](#)). Following training on the use of the equipment at Visit 2, subsequent refresher training should be provided if required
16. [REDACTED]
Following training on completion of the diary at Visit 2, subsequent refresher training should be provided if required
17. [REDACTED]
18. [REDACTED]
19. Biobanking sampling requires a consistent status from one sample to another in terms of fasting vs non-fasting; a fasting status is therefore defined. Sampling is optional and requires separate informed consent. Refer to Section [5.5](#)
20. [REDACTED]

[figure not shown]
21. After the EoS visit (= individual patients end of the trial) the Investigator should report only any cancers of new histology and exacerbations of existing cancer, trial medication related Serious Adverse Events (SAEs) and trial medication related Adverse Events of Special Interest (AESIs) of which the Investigator may become aware of and only via the BI SAE form (refer to Section [5.2.6.2.1](#))
22. The physical examination at Visit 1a should include an assessment of the clinical criteria for Child-Turcotte-Pugh classification (refer to Appendix [10.3](#))

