6.1 VISIT SCHEDULE

All visits should be scheduled according to the [Flow Chart](#). Each visit date (with its permitted time window) should be calculated in relation to the day of randomisation (i.e. Day 1). During the dose titration period of the trial (i.e. from Visit 2 [randomisation] to Visit 4), scheduled trial visits must be at least 7 days apart, since a patient must have taken the preceding dose for at least 7 consecutive days before up-titration occurs (refer to Section [4.1.4](#)). For this reason, if the permitted time window (+2 days) is applied to Visit 3, the permitted time window must also be applied to Visit 4 (+2 days). Missed visits should be re-scheduled as soon as possible ideally within the permitted time window for that visit. If any visit has to be rescheduled, subsequent visits should follow the original visit schedule. Unscheduled visits can be performed at the discretion of the Investigator at any time for safety reasons or, for instance, to provide trial medication (e.g. a re-start following treatment interruption).

All visits will take place at the investigational site, and ideally they should be performed in the morning. In the randomised treatment period, on the morning of a visit, the trial medication will be administered as part of the visit. Therefore, on these days, patients should be instructed not to take their morning dose in advance of their clinic visit (refer to Section [4.1.4](#)).

status of a patient should be in accordance with the [Flow Chart](#) and will be recorded in the eCRF. Patients who fail to follow the afore-mentioned instructions should have the visit re-scheduled as soon as possible, ideally on the following day.

In the event of force majeure or other disrupting circumstances (refer to [Section 6](#)), physical patient visits to the sites may not be feasible or may need to be restricted to ensure patient safety. Based on a thorough assessment of the benefits and risks, the following visits may be performed at the patient's home, remotely (by phone) or as a combination of home and remote visits:

- Visit 6
- Visit 9

- Visit 10

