6.2 DETAILS OF TRIAL PROCEDURES AT SELECTED VISITS

At each visit, assessments should be performed as indicated in the [Flow Chart](#) and as detailed in Section [5](#).

In the randomised treatment period, all assessments should be performed before the trial medication is taken. Exceptions to this are post-dose vital signs and ECGs, [REDACTED] [REDACTED] Once the trial medication is administered / once all visit assessments are complete that require a fasting status, patients may eat as normal [REDACTED].

Vital signs measurements should always precede the ECG, and the ECG should always be measured before any blood samples are taken (refer to the [Flow Chart](#) and Sections [5.2.2](#) and [5.2.4](#)).

In the event of force majeure or other disrupting circumstances the visits indicated in Section [6.1](#) may have to be performed at the patient's home, remotely (by phone) or as a combination of home and remote visits. At these visits, the following assessments can be performed at the patient's home or remotely:

- concomitant therapy
- pregnancy testing (urine)
- IRT call
- dispense trial medication
- train patient / provide refresher training / dispense / review results (home BP and HR monitoring; [REDACTED])
- all AEs / SAEs / AESIs
- compliance check

Trial medication will not be collected at visits performed remotely. Instead, the medication should be collected when the patient next visits the site, or when a visit is performed at the patient's home (see below).

The following assessments can be performed at the patient's home:

- anthropometric measures
- vital signs
- physical examination
- resting 12-lead ECG (using a portable ECG machine)
- safety laboratory sampling and review of results
- collect trial medication

If safety laboratory sampling via the central laboratory is not possible from the investigational site (and is instead performed at the patient's home), analyses can be performed at a local laboratory. The results of the safety laboratory tests must be transferred to the Investigator who must ensure a medical review and document any clinically relevant safety issues as AEs. For a list of "minimum required safety laboratory parameters" refer to Section [5.2.3](#) and Table [5.2.3; 2](#).

All deviations from the original schedule of assessments as defined in the [Flow Chart](#) will be documented and the implications considered for the analysis of the trial data.

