6.2.2.1 End of Treatment / Early Discontinuation visit

Patients who successfully complete the entire 24 week treatment period should have the assessments for the EoT visit performed as indicated in the [Flow Chart](#). Such patients should be registered as completed in the IRT system. End of trial medication must also be recorded on the corresponding eCRF.

For patients who discontinue trial medication prematurely (for whatever reason), an ED visit (refer to the [Flow Chart](#)) should be completed instead of the planned treatment period visit (refer to Section [3.3.4](#)). Ideally the ED visit should be performed within seven days of discontinuing the trial medication. The assessments performed at the ED visit should be in accordance with the [Flow Chart](#), with the following exceptions:

- HVPG: not required
- [REDACTED]
- [REDACTED]
- biobanking sampling: not required

Patients who discontinue treatment early should be registered as discontinued in the IRT system. End of trial medication must also be recorded on the corresponding eCRF.

At the EoT and / or ED visit, patients should be reminded about restrictions (refer to Section [4.2.2](#)) that still need to be observed up until the EoS visit (refer to Section [6.2.3](#)). Home BP and HR monitoring should continue between the EoT / ED visit and the EoS visit.

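### As machine-read, the Flow Chart has no urine pregnancy test after Week 12, although a laboratory-table footnote requires one every 4 weeks; a site following the chart would schedule none for the last 12 weeks of dosing

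*Protocol*

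**What the plan says.** Protocol Table 5.2.3: 1 lists a urine pregnancy test, and its footnote 9 sets the timing: "WOCBP only, Visit 2 onwards. Measured locally at the site every 4 weeks using a pregnancy test kit provided by the central laboratory". It gives no end visit.

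The Flow Chart has a separate row for pregnancy testing. As machine-read, it shows a serum test at Visit 1a, urine tests at Visits 2, 5, 7 and 8, and blanks at Visits 9, 10, EoT/ED and EoS.

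The two places refer to each other. Section 5.2.3 says of the safety laboratory parameters: "Sampling time points will be as indicated in the" Flow Chart. The Flow Chart's own footnote 9 gives no testing interval and points the other way: "Pregnancy testing at dosing visits should be completed prior to administration of trial medication. Refer to Section" 5.2.3.

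Three other provisions bear on the point:

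- Section 6.1 says of disruptive circumstances: "Based on a thorough assessment of the benefits and risks, the following visits may be performed at the" patient's home or remotely, and it names Visits 6, 9 and 10. Section 6.2 includes urine pregnancy testing among the assessments that can be done at those visits.
- Section 6.2.2.1 on early discontinuation: "The assessments performed at the ED visit should be in accordance with the" Flow Chart, apart from listed exceptions.
- Flow Chart footnote 3 on the end of dosing: "The last dose of trial medication will be administered in the evening of the day before the EoT visit".

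**The concern.** A schedule followed as drawn leaves out tests that another rule in the same protocol requires. Table 1.4.2: 3 names pregnancy testing, together with contraception, as the mitigation for embryo or foetal exposure. Section 3.3.4.1 makes pregnancy a reason to stop trial medication. Trial medication is still dispensed at Visits 9 and 10, and the chart shows no pregnancy test at either.

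The missing tests do different jobs. Tests at Weeks 16 and 20 could stop exposure. A test at EoT or ED could not, because the last dose has already been taken. It could only reveal exposure that has occurred, so that it is reported within 24 hours and followed up as Section 5.2.6.2.3 requires.

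**Working it through.** The plan gives no figure to reproduce, so the check compares two schedules.

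**Inputs.** Visit days and weeks come from the Flow Chart header. The charted tests come from its pregnancy row, which splits into 14 cells for 14 visit columns, as do the HVPG, ultrasound and safety laboratory rows. The 4-weekly rule is footnote 9 of Table 5.2.3: 1.

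| Visit | Week | Day | Footnote 9 | Flow Chart |
|---|---|---|---|---|
| 2 | 0 | 1 | test | test |
| 5 | 4 | 29 | test | test |
| 7 | 8 | 57 | test | test |
| 8 | 12 | 85 | test | test |
| 9 | 16 | 113 | test | blank |
| 10 | 20 | 141 | test | blank |
| EoT | 24 | 169 | test | blank |
| EoS | 28 | 197 | test, if read literally | blank |

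**Last dose.** This is the evening before EoT: Day 169 − 1 = Day 168, giving 168 planned dosing days.

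**Tests after Day 1 and before the last dose.** Footnote 9 gives 5 (Days 29, 57, 85, 113, 141). The chart gives 3 (Days 29, 57, 85). So 2 of 5, or 40%, are uncharted. EoT/ED is a further uncharted test, for detection only.

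**Longest planned dosing stretch after a test.**
- Chart: 168 − 85 + 1 = 84 days, and 84/168 = 50% of dosing.
- Footnote 9: 113 − 85 = 28, 141 − 113 = 28, and 168 − 141 + 1 = 28 days.

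**Most dosing a positive test could spare, per affected woman.** At Week 16, 168 − 113 + 1 = 56 days. At Week 20, 168 − 141 + 1 = 28 days.

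**Which schedule the protocol appears to intend.** Among the home/remote Visits 6, 9 and 10, the chart places a urine test at 0 of 3. Footnote 9 places one at 2 of 3 (Visits 9 and 10; Week 6 is not a 4-weekly point). The Section 6.2 entry has a scheduled use only under footnote 9. Footnote 5 of the same table expressly excludes Visits 9, 10 and EoS for aldosterone and renin, whereas footnote 9 excludes no later visit.

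**Scale of the risk.** Section 3.3.2 requires contraception with a failure rate below 1% per year when used consistently and correctly. Over 84 days that is below 1% × 84/365 = 0.23% per woman. The number of WOCBP is not given. Even if all 2 × 26 = 52 patients on active drug were WOCBP, an extreme assumption, fewer than 52 × 0.0023 = 0.12 pregnancies would be expected under correct use. Imperfect use would raise this.

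**The case against.** The strongest objection is that the blanks may not exist in the source. A full count of cells shows that the grid survived the reading of the PDF, not that every mark in it did. The Section 6.2 entry makes lost marks at Visits 9 and 10 plausible. This stands, and it makes the point conditional.

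A reader might infer that the circular references leave neither place in charge. The documents do not support that. Section 5.2.3 expressly hands sampling times to the Flow Chart, while the chart's footnote returns the reader to 5.2.3 without giving an interval. On that reading the chart governs and footnote 9 is out of line. The conflict remains, because footnote 9 then states an interval that the governing schedule does not deliver.

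It can also be said that sites will find the 4-weekly rule, since the chart's footnote leads them to the section that holds it, and that the safety laboratory row is marked at Visits 9, 10, EoT/ED and EoS. The first part stands: omission is possible, not certain. The second does not settle the matter, because pregnancy testing has its own row.

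Finally, the risk is small. Contraception is mandatory, known pregnancies must be reported whatever the schedule, and Section 1.2.2 reports no drug-related effects on embryo-foetal mortality, foetal growth or malformation in the animal studies. That limits the weight of the point without removing the inconsistency.

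**Conclusion.** The inconsistency holds in the text as supplied. A site following the Flow Chart would test at Day 85 and then dose to Day 168 with no further scheduled test: 84 days, against at most 28 under footnote 9. Two of five tests that could stop exposure are uncharted, as is the EoT/ED test, which could only detect it. Footnote 9 and the home/remote provision indicate that 4-weekly testing is intended.

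This assumes that the machine-read row is right and that patients attend on the planned days. Confidence is medium until the row is checked. A reader might infer that women will go untested or that a number of exposures can be predicted. Neither follows: sites can reach the 4-weekly rule, and the number of WOCBP is unknown. The effect is confined to patient safety monitoring; no endpoint or analysis changes. Correction is worthwhile because it is cheap and removes conflicting safety instructions.

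**What to change.** 1. Check the Flow Chart pregnancy row against the source PDF.
2. If the blanks are real, add a urine test (x_u) at Visit 9 (Week 16), Visit 10 (Week 20) and EoT/ED.
3. State the end visit in footnote 9 of Table 5.2.3: 1, for example: WOCBP only, every 4 weeks from Visit 2 through EoT/ED.
4. Say openly whether EoS (Week 28) is included. The current footnote has no end and so reaches it; ending at EoT/ED would drop that test. Contraception is required only until 7 days after the last dose (168 + 7 = Day 175), which is 197 − 175 = 22 days before EoS, so ending at EoT/ED is a reasonable choice if it is stated.

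The home/remote list in Section 6.2 can stay as it is. The cost is one Flow Chart row, one footnote and up to three urine kits per WOCBP (four if EoS is included), all at visits already scheduled.
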